## **6.6 Definition of Enrollment Into the Study.**

The participants who have consented into the study at the beginning of the screening visit are all considered to be enrolled. All participants who meet inclusion criteria, are randomized into a treatment allocation group, and receive their treatment will be included in the a-priori analyses for Aim 3 and for the radiographic findings for Aim 4.

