## **6.5 Traction Therapy.**

Our OT will create a customized hand-based orthosis that allows convenient application of finger traps. The most symptomatic DIP and any other digit that the participant requests will have a finger trap customized to that digit.

The resting hand orthosis will be fabricated using standard materials available in the Occupational Therapy Clinic. This will involve the use of a 1/8 inch low stretch and low memory material (e.g. Manosplint Wisconsin or Performance Health Polyflex). Our OT will draw a pattern for the orthosis at 1cm around the hand of interest, stopping just proximal to the wrist crease and extending radially to the thumb metacarpophalangeal joint. The center of the thumb flap will be cut out to form a thumb hole component for proximal stabilization of the orthosis. Our OT will then mold the orthosis to the volar hand with care to accommodate for palmar arches and to extend all fingers to a comfort position. Our OT will then flare the proximal edge of the orthosis to limit pressure on the volar forearm soft tissue. The strapping is then looped through the thumb hole component and attached at the palm obliquely over the phalanges. Soft padding will be added to the orthosis under the phalanges for comfort.

The traction orthosis is identical to the resting hand orthosis with the exception that there is an addition of finger traps that will be applied to the orthosis. The finger traps used in this study will be manufactured by Instrument Specialists, Inc (ISI). Finger traps have already received FDA approval under the Code of Federal Regulations, Title 21, Volume 8 (21CFR890.5925), Revised April 2016.

Title 21 – Food and Drugs

Chapter 1 – Food and Drug Administration, Department of Health and Human Services

Subchapter H – Medical Devices

Part 890 – Physical Medicine Devices

Subpart F – Physical Medicine Therapeutic Devices

Sec. 890.5925 Traction Accessory

(a) Identification. A traction accessory is a nonpowered accessory device intended for medical purposes to be used with powered traction equipment to aid in exerting therapeutic pulling forces on the patient's body. This generic type of device includes the pulley, strap, head halter, and pelvic belt.

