## **7.2 Discontinuation of Study Intervention**

The PI may discontinue a participant from the study for the following reasons:

- Inability to fit the hand orthosis after a good will effort by the participant and our OT.
- Pregnancy
- If any clinical adverse event (AE) occurs such that continued participation in the study would not be in the best interest of the participant
- If early termination of the study is deemed necessary

At the time that the orthosis is created and customized for the participant, our OT will provide instruction on how to don the orthosis and how to remove the orthosis. She will also provide instruction to the participant that if the finger trap is uncomfortable and difficult to remove, there is always the option of cutting the finger trap off the finger with a pair of scissors. Our OT will observe the participant donning and removing the orthosis in the clinical setting to verify that the participant has good understanding of how to perform these activities. She will also review with the participant how to cut the finger trap off in the setting that the participant is unable to remove the finger trap. She will also provide the participants with a handout describing these activities that participants can take with them. If the participants still have difficulty donning and/or removing the orthoses, the participants will be instructed to contact our OT to schedule an as needed appointment to review how to perform these activities.

We will do our best to minimize any discomfort related to these orthoses as our OT will make every effort to address any discomfort the participants may complain of at the time that the orthoses are created by modifying or adjusting the orthoses. Also, we will schedule all participants to return for a 2 and 4 week follow up visit with our OT to assess for appropriate fit and to address any concerns the participants might have related to the orthoses. If these issues cannot be satisfactorily resolved, then the participants will be given an option to terminate use of the orthosis.

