Discontinuation from the study intervention does not mean discontinuation from the study, and remaining study procedures will be completed as indicated by the study protocol. If a clinically significant finding is identified (including, but not limited to changes from baseline) after enrollment, the investigator or qualified designee will determine if any change in participant management is needed. Any new clinically relevant finding will be reported as an adverse event (AE).

A dedicated Case Report Form (CRF) administered on RedCap entitled “Early Termination Form” will be completed by our research coordinator to capture the date and the specific underlying reason for termination from study intervention.

Subjects who sign the informed consent form and are randomized but do not receive the study intervention will still be included in the baseline demographics description. Missing outcomes among participants who missed pain and function questions or lost to follow up will be addressed by multiple imputation using the Markov chain Monte Carlo method. Under the assumption of missing at random, we will include factors which may be related to missing of outcome in the imputation, such baseline demographic characteristics, disease severity, etc. We can use this method of imputation because all outcomes are continuous and they can be assumed to follow multivariate normality distribution. To use this method of multiple imputations, there is an assumption of missing at random. Though this assumption is not testable, multiple imputation method are viewed as less biased than a completers’ analysis, last observation carried forward, and single imputation method. Subjects who sign the informed consent form, and are randomized and receive the study intervention, and subsequently withdraw, or are withdrawn or discontinued from the study, will not be replaced.

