We will complete descriptive analyses of baseline characteristics of the treated and control groups to allow assessment of generalizability and success of randomization. We will use either Student t-tests or rank-based nonparametric tests where appropriate. Our primary analytic approach will be to use intention- to-treat (ITT) analyses to compare mean change of each symptom and function outcome during follow-up between traction therapy and the control groups with linear regression model for longitudinal repeated measures data. Missing outcomes among participants who missed pain and function questions or lost to follow up will be addressed by multiple imputation using the Markov chain Monte Carlo method. Under the assumption of missing at random, we will include factors which may be related to missing of outcome in the imputation, such baseline demographic characteristics, disease severity, etc. We can use this method of imputation because all outcomes are continuous and they can be assumed to follow multivariate normality distribution. To use this method of multiple imputations, there is an assumption of missing at random. Though this assumption is not testable, multiple imputation method are viewed as less biased than a completers' analysis, last observation carried forward, and single imputation method.

**Specific aim 4. Imaging outcomes.** Given the exploratory nature of this study, we will be broad in our inclusion of outcome measures we will evaluate. The primary structural outcome measure will be change in sum of the Kellgren and Lawrence score of all DIPs in the hand that was braced. We will also evaluate change in joint space narrowing, and osteophyte scores and the Verbruggen-Veys from baseline to 6 month follow up comparing the traction versus the control groups. For those randomized to traction, we will also compare the hand that received traction to the hand that did not. To address potential missing data, we will use a multiple imputation method, assuming the data are missing at

random. We will perform an ANOVA to compare mean change in the sum of radiographic scores over the 6 month follow up period between the traction therapy and the control groups. If there are unbalanced baseline covariates between the treatment groups, we will use an ANCOVA approach to include them as covariates in the analysis.

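### The plan promises intention-to-treat for Aim 3, but section 6.6 ties the Aim 3 and Aim 4 radiographic analyses to receiving treatment, an undefined event after randomisation

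*Combined protocol and SAP*

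**What the plan says.** Section 9.0, under Specific aim 3, states: "Our primary analytic approach will be to use intention- to-treat (ITT) analyses". It applies this to the change in each symptom and function outcome and names no exception. Under Specific aim 4 the same section says "We will perform an ANOVA to compare mean change in the sum of radiographic scores" and adds multiple imputation, but names no analysis population.

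Section 6.6 covers both aims. It takes eligible people who "are randomized into a treatment allocation group, and receive their treatment will be included in the a-priori analyses for Aim 3"; the same rule covers the Aim 4 radiographs.

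Section 7.2 deals with the untreated. Those who are "randomized but do not receive the study intervention will still be included in the baseline demographics description"; no outcome analysis is mentioned for them. The no-replacement rule is written for those who "are randomized and receive the study intervention, and subsequently withdraw, or are withdrawn or discontinued from the study, will not be replaced". The same section also says "Discontinuation from the study intervention does not mean discontinuation from the study, and remaining study procedures will be completed".

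**The concern.** Intention-to-treat means that everyone randomised is analysed in the assigned arm. Section 6.6 adds a condition that can only be met after allocation, because section 4.3.a places the making of the orthosis after randomisation. Read as written, that is a modified intention-to-treat set.

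The plan does not say whether receipt means that the orthosis was made, fitted, taken home or worn. Section 6.4 says that controls are offered a resting orthosis, and it does not say how a refusal counts. Section 7.2 foresees "Inability to fit the hand orthosis after a good will effort by the participant and our OT" as a reason for discontinuation. Non-receipt could differ by arm. Section 6.5 says "The traction orthosis is identical to the resting hand orthosis with the exception that there is an addition of finger traps", so traction has one more fitting step, and the therapist who fits the device is unblinded (section 6.3).

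Table 2 in section 3.0 places the primary symptom and primary structure endpoints in these two analyses. If anyone is never fitted, the analyst would have to choose the population after the fact. Section 2.8 intends the pilot's effect sizes to feed the power calculation of the follow-up trial, so the choice would carry forward.

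**Working it through.** **Text comparison**

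| | Aim 3 (symptoms, function) | Aim 4 (radiographs) |
|---|---|---|
| Section 9.0 | Intention-to-treat, no exception | ANOVA and multiple imputation, no population named |
| Section 6.6 | Eligible, randomised, treated | Eligible, randomised, treated |
| Section 7.2, randomised but untreated | Baseline description only | Baseline description only |

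Aim 3 therefore has two populations. Aim 4 has one rule, and it depends on an event after randomisation. Participants who receive an orthosis and later stop are in both sets, so they are not affected.

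**The plan's own figure.** Section 9.0 gives at least 80% power for a 1.7-point difference with SD 3, 50 per arm and two-sided 5%. SE = 3 × √(2/50) = 0.60 and 1.7/0.60 = 2.83. Normal-approximation power is 80.9% and t-test power is 80.1%, so the figure reproduces. Only the SD of 3 and the 1.7 are used below. That statement assumes 100 participants while 40 are planned, which is a separate matter.

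**Size of a possible shift.** Inputs: 40 participants (section 4.1), taken as 20 per arm; SD 3 for the radiographic sum score (section 9.0). Assumed, because the documents do not give them: SD 25 for the pain VAS; k, the number excluded per arm; and the gap, meaning how much worse the excluded do than those analysed.

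Shift = (k in traction − k in control)/20 × gap, when the gap is the same in both arms.

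- *Aim 4:* SE = 3 × √(2/20) = 0.95. One excluded from one arm, gap 1 to 3 points: 1/20 × 1 = 0.05 to 1/20 × 3 = 0.15. Three excluded: 0.15 to 0.45. In SE units the range is 0.05/0.95 = 0.05 to 0.45/0.95 = 0.47.
- *Aim 3 VAS:* SE = 25 × √(2/20) = 7.9. One excluded, gap 10 to 30: 0.5 to 1.5 points. Three excluded: 1.5 to 4.5. In SE units the range is 0.5/7.9 = 0.06 to 4.5/7.9 = 0.57.
- *None excluded, or equal numbers with equal gaps:* 0.

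The sign follows the arm that loses its poorer responders. Losing them from traction flatters traction, and losing them from control does the reverse.

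**Type I error.** Simulation of 200,000 trials per case: 20 per arm, no treatment effect, the same k poor-prognosis participants in each arm, and a t-test standing in for the planned models.

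| Case | VAS (SD 25) | Radiographic sum (SD 3) |
|---|---|---|
| Dropped from both arms | about 0.050 | about 0.050 |
| One dropped, one arm only, any gap above | about 0.050 | about 0.050 |
| Three dropped, one arm only, largest gap | about 0.069 (gap 30) | 0.063 to 0.064 (gap 3) |

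**Price of the alternative.** If a never-treated traction participant gains no traction effect and is analysed as assigned, a true 1.7 becomes 1.7 × (1 − k/20). That is 1.62 for one such participant, 1.53 for two and 1.45 for three.

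**The case against.** Section 6.6 is about enrolment. It says who will be included, not that only they will be. Section 9.0 is the statistical section and names intention-to-treat outright, so an analyst following it has no choice to make for Aim 3. For Aim 4 there is no contradiction, because section 9.0 never claims intention-to-treat there.

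The window for non-receipt is also narrow. Allocation reaches the therapist only after the other baseline care (section 10.7.a), the orthosis is made at the same visit (section 4.3.a), and several trap sizes are on hand (section 6.5). Many fitting failures may emerge only after an orthosis has been supplied, and those participants stay in the set. The error rate of 0.069 needs 3 of 20 (15%) never fitted in one arm only, with a gap of 1.2 assumed SDs. Groups also stay masked as A and B during the primary analyses (section 6.3).

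Most of this stands as a limit on size. It does not remove the conflict. If everyone randomised were meant, the receipt condition in section 6.6 would have no purpose. Section 7.2, by saying that the untreated still enter the baseline description, implies that they leave the rest. Section 9.0 cannot settle Aim 4, where it names no population. Multiple imputation fills in outcomes within an analysis set and does not define that set. Masking limits a selective choice between populations, but an analyst would still have to make the choice.

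One further point is fair. The dilution figures assume that the untreated participants' outcomes are observed. If they do not return, imputation that ignores receipt would treat them like their treated arm-mates.

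**Conclusion.** The concern holds. For Aim 3, sections 6.6 and 9.0 give different populations. For the Aim 4 radiographs, the only rule conditions the primary structure analysis on an undefined post-randomisation event. It should be fixed before the data are analysed.

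The likely size is nil to modest. It is zero if everyone is fitted, which the visit plan makes plausible. Under the assumed one to three exclusions in one arm it is 0.05 to 0.45 radiographic points or 0.5 to 4.5 VAS points in either direction, always below 0.6 of a standard error. The documents give no never-treated rate, prognosis gap, VAS SD or direction, so these figures show scale and do not predict a bias. The conflict itself rests on the text alone.

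**What to change.** Replace the population sentence in section 6.6, and align sections 7.2 and 9.0 with it: *All randomised participants will be analysed in their assigned arm for Aim 3 and for the Aim 4 radiographs, whether or not an orthosis was received.*

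In section 7.2, state that continued outcome collection, the planned multiple imputation and the no-replacement rule also cover participants who never received an orthosis. Say whether receipt enters the imputation model. If a received-treatment analysis is kept, label it a sensitivity analysis and give one definition of receipt for both arms. Report the number never fitted, by arm, in the CONSORT diagram already planned in section 10.10.a.

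The cost is a few sentences across the three sections. No participants, visits or images are added, because the week 4, 12 and 24 assessments and the week 24 radiographs are already scheduled. The drawback is the dilution shown above, 5% of the traction effect for each never-treated traction participant who gains nothing.

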#### **4.3 Subject Participation Duration**

##### **4.3.a Study Participation Duration:**

- **Week -1:** Screening Visit (phone or email) (10 - 20 minutes) – Assess preliminary eligibility criteria
- **Week 0:** Eligibility/Baseline Visit (6 hours) – assess eligibility criteria, obtain informed consent, all clinical outcome assessments, hand x-rays, prescreening assessment for MRI, hand therapist will provide non-pharmacologic therapies for hand OA, randomization allocation, creation of hand orthosis based on randomization allocation.
- **Week 2:** Study Visit (0.5 – 3 hours) – All participants: hand therapist assess orthosis fit; for selected 10 people: proof of concept X-rays, with and without orthoses in place AND MRI of one finger DIP
- **Week 4:** Study Visit (1.5 hours) – all clinical outcome assessments, hand therapist assess orthosis fit.
- **Week 4 – 6:** Study Visit (0.5 hours) – MD visit if requested.
- **Week 12:** Study Visit (1 hour) – all clinical outcome assessments.
- **Week 24:** Study Visit (3-4 hours) – all clinical outcome assessments, bilateral hand X-rays, follow up MRI (if it was done at week 2).

**4.3.b Study Duration:** The estimated time between when study opens for enrollment and final data collection occurs is 18 months. The estimated time between when study opens for enrollment and final data analysis is completed is 30 months.

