## **6.2 Randomization.**

Our Research Coordinator will contact our Statistician, [name], who will provide randomization allocation. [name] will use a macro in SAS that uses CALL RANUNI and PROC PLAN to generate permuted blocks of randomization stratified by sex.

- He will create a designation of group A v. group B, without knowing which group represents the intervention and the control.
- He will use block sizes of 4 for this process.

[name] will then communicate to our Research Coordinator and our OT that the treatment allocation has been entered onto RedCap.

Our statistician, [name], and our research coordinator will be blinded to treatment assignment. Only our OT will be unblinded to treatment allocation.

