Although hand OA is very common, only a small percentage seek care from their providers for this condition. Therefore, engagement into medical care for hand OA will be useful as a retention strategy. Additionally, participants will all receive durable goods to provide the standard of care for hand OA including a thermal modality and the orthoses made for them by our OT. Also, they will be instructed on range of motion exercises and joint protective strategies that should help their hand symptoms.

Regarding special vulnerable populations, fetuses, neonates, and children will not be eligible for this study because we are targeting veterans who are patients at the MEDVAMC. Pregnant women will be excluded to mitigate any potential risks related to radiation exposure associated with obtaining radiographs and high powered magnetic fields related to obtaining MRIs. We do not expect that prisoners or institutionalized individuals will learn about this study and therefore will not be recruited into the study. Therefore, no vulnerable populations will be included in this study so none of these groups will be placed at increased risk relative to other participants included in our study.

Once a participant is deemed eligible for participation into the study and is consented for the study, he/she will have all his/her baseline assessments administered by the study research coordinator. After this is completed, the research coordinator will email [name], our statistician, who will generate a randomization assignment (designated as group A v. group B) stratified by gender. This allocation assignment will only be transmitted to our OT by email after the OT has also seen the participant at baseline and provided all other non-pharmacologic interventions for hand OA that are considered standard of care. Prior to the beginning of the study, the OT will use a coin flip to decide which group (A v. B) will be the treatment v. control group. The OT will be the only person in the investigative team to know this

designation until the study data set is closed and all analyses are finalized. At that point, the OT will customize the appropriate orthosis for the participant to take with him/her.

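### Section 6.6 ties the Aim 3 analysis set to receipt of treatment, so the analysis that section 9.0 calls intention-to-treat is, as written, modified ITT

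*Combined protocol and SAP*

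**What the plan says.** Three places bear on who is analysed.

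- Section 6.6 (Definition of Enrollment Into the Study) sets the population: eligible participants who "are randomized into a treatment allocation group, and receive their treatment will be included in the a-priori analyses for Aim 3". The sentence goes on to cover the radiographic part of Aim 4.
- Section 7.2 (Discontinuation of Study Intervention) says that participants "randomized but do not receive the study intervention will still be included in the baseline demographics description". It names no outcome analysis for them. It deals separately with those "randomized and receive the study intervention, and subsequently withdraw, or are withdrawn or discontinued from the study, will not be replaced".
- Section 9.0 (Statistical Considerations), under Aim 3, says: "Our primary analytic approach will be to use intention- to-treat (ITT) analyses to compare mean change of each symptom and function outcome". For the Aim 4 radiographs it plans an ANOVA and gives no population label.

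The plan does not define ITT, does not use the term modified ITT, and does not say which section governs if they differ.

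On timing, the week 0 entry in section 4.3.a ends with "randomization allocation, creation of hand orthosis based on randomization allocation". Section 10.7.a adds: "This allocation assignment will only be transmitted to our OT by email after the OT has also seen the participant at baseline". Section 6.2 says: "Only our OT will be unblinded to treatment allocation".

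**The concern.** An ITT comparison keeps everyone in the arm to which they were randomized, whatever happens next. A condition on receiving treatment removes people by an event that occurs after randomization. If that event is more likely in one arm, or involves different kinds of participant in the two arms, the groups compared are no longer the groups that randomization produced.

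The event here is a fitting done by the one person who knows the allocation, and the devices differ. Section 6.5 says: "The traction orthosis is identical to the resting hand orthosis with the exception that there is an addition of finger traps". The traction arm therefore has an additional component to fit and tolerate.

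Two of the pilot's purposes are touched. Section 2.8 intends its effect sizes to feed the power calculation for the follow-up R01, so the estimate should be what its label says. Feasibility is Aim 1, and a participant who could not be fitted is an informative result of assignment to traction, not someone to leave out of Aim 3.

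**Working it through.** **Comparing the texts**

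| Participant | Section 6.6 | Section 7.2 | ITT as named in 9.0 (Aim 3) |
|---|---|---|---|
| Randomized, treated, completes | in | – | in |
| Randomized, treated, later stops | in | not replaced | in |
| Randomized, never treated | condition not met | baseline description only | in |

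Only the last row conflicts. The word *only* is absent from 6.6, so the restriction is a reading of the text. It is the natural reading: the receipt condition has no function unless it leaves someone out, and 7.2 names only a baseline use for that same group. The multiple imputation in 7.2 and 9.0 is described for missed questions and loss to follow-up. It does not mention participants who were never treated.

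The other condition in 6.6, meeting the inclusion criteria, is assessed before randomization and does not raise this problem.

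**When receipt is decided**

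Under 10.7.a, the statistician generates the assignment after the baseline assessments. It goes to the OT once the other non-pharmacologic care has been given, and the OT then makes the assigned orthosis. Exclusion that depends on arm can arise only between that transmission and the end of the fitting.

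**Size, as an illustration**

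The plan has no figure on this point. Its only power statement (section 9.0: 50 per arm, difference 1.7, SD 3, at least 80%) concerns the radiographic score. It reproduces (0.809 by normal approximation, 0.801 by t-test) and plays no part here.

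Inputs:
- Total of 40 (section 4.1). Twenty per arm is assumed, since the ratio is not stated; section 6.2 gives blocks of 4.
- kT and kC, the never-fitted participants in the traction and control arms: assumed.
- d, the points on a 0–100 VAS by which their outcome is worse than the rest of their arm: assumed, 10 to 30.

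Removing k of 20 participants whose mean is worse by d improves the arm mean by k × d / 20. The shift in the group difference toward traction is therefore (kT − kC) × d / 20.

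| kT, kC | d = 10 | d = 20 | d = 30 |
|---|---|---|---|
| 1, 0 | 0.5 | 1.0 | 1.5 |
| 2, 0 | 1.0 | 2.0 | 3.0 |
| equal | 0 | 0 | 0 |

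The sign reverses if the never-fitted participants do better than the rest of their arm, or if only control is affected.

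Effect on precision, with equal SDs: the standard error ratio is √[(1/(20 − k) + 1/20) / (2/20)].
- k = 1: √1.0263 = 1.013, a rise of 1.3%.
- k = 2: √1.0556 = 1.027, a rise of 2.7%.

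For scale, the documents give no VAS SD. If it were 20 to 30, the standard error of the difference would be SD × √(2/20), or 6.3 to 9.5 points. The largest shift in the table is 3.0/6.3 = 0.48 of a standard error at SD 20 and 3.0/9.5 = 0.32 at SD 30.

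**The case against.** The strongest defence is that the excluded group may be empty. Randomization, fitting and supply all fall within one baseline visit. Section 6.5 provides a range of finger-trap sizes and sizes each trap individually. Both arms' treatment includes standard care, so it could be argued that every randomized participant receives something. Section 6.6 is headed as a definition of enrollment and does not say *only*, whereas section 9.0 is the statistical section and says ITT. The illustration uses assumed inputs and stays under half a standard error, in a pilot that leaves efficacy to a later trial.

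Most of this stands as a limit on size. It does not remove the mismatch. Section 7.2 provides for participants who are randomized and do not receive the intervention, so the plan treats that group as possible, and two analysts could build different Aim 3 datasets from the same text.

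Several stronger readings are tempting and are not supported:
- *Participants who stop wearing the orthosis are dropped.* They have received treatment, so 6.6 includes them, and 7.2 says that stopping the intervention does not end study participation.
- *The fitting-failure reason in 7.2 shows that some participants will never be treated.* It is listed under discontinuation, after effort by participant and OT, and reads at least as well as failure after supply.
- *The Aim 4 radiographic analysis breaks an ITT promise.* Section 9.0 makes no such promise there.
- *Untreated participants will be replaced.* The no-replacement sentence does not mention them; nothing says that they will be.

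**Conclusion.** The point holds in a narrow form. As written, the primary Aim 3 analysis uses a modified-ITT set under an ITT label, and the condition that makes it so operates after randomization, at an unblinded fitting that differs between arms. This rests on reading 6.6 as restrictive, which its wording and 7.2 support but do not state outright.

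The number affected is probably very small and could be zero. A reader might infer that the rule favours traction. The documents do not support that: they give no rate of failed fitting and no outcomes for such participants, so size and direction are unknown. The 0.5 to 3.0 points are an illustration of one scenario. Precision is barely affected; the issue is comparability of the arms and an accurate label. It should be corrected because the correction costs almost nothing.

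**What to change.** In section 6.6, delete the condition on receiving treatment, so that all randomized participants, including any never fitted, are followed and analysed in their assigned arm. In section 7.2, change the sentence on randomized but untreated participants so that it places them in the outcome analyses as well as the baseline description. If a treated-only analysis is wanted, keep it as a labelled sensitivity analysis.

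Use the same all-randomized set for the Aim 4 radiographs. One clause in 6.6 governs both aims, and separate populations would serve no purpose.

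The cost is two wording edits. The week 4, 12 and 24 assessments and the 24-week radiographs are already scheduled for all participants, so no visits or procedures are added.
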